Objectives: Reiki is an energy-based healing therapy using light touch. Manual therapy is a technique using light effleurage. These complimentary healing services are utilized to promote relaxation, sleep, improve emotions, and decrease pain. After reviewing the Reiki research literature, more research is required since sample sizes were small, subjects were generally healthy (not hospitalized), and subjects had multiple medical backgrounds. Only 1 study focused on cardiac surgery patients. In the current research study, we aim to learn if Reiki and manual therapy enhances postoperative clinical outcomes for patients after first time coronary artery bypass graft (CABG) and/or cardiac valve surgery. **Design and Methods:** A randomized, controlled non-blinded study will be used. The sample size (272 total; 136 per group) was based on a power analysis using the primary outcome. The intervention group will receive usual care plus Reiki and manual therapy, with Reiki being delivered first. Hand placements include: head, chest, shoulders, hands, knees, and feet for 15 minutes. Manual therapy will consist of light effleurage to the head and feet for 5 minutes. Total therapies time is 20 minutes. Reiki and manual therapy will be delivered for 3 consecutive days beginning on the day after endotracheal tube removal. The usual care group will receive rest, which is part of usual postoperative care. There will not be a sham-treatment group, based on previous research findings when a sham group was used. **Outcome Measures:** depression and anxiety (*Brief Symptom Inventory*, 12-item self-administered tool); pain (self-reported and recorded in EPIC by staff nurses as part of usual care -- 0 [no pain] - 10 [worst pain] scale), highest (worst) and lowest (least) pain in the past 24 hours will be assessed; night time sleep (Richards-Campbell Sleep Questionnaire; 5 item self-administered tool)—to be measured at baseline and after the last Reiki/manual therapy treatment or 3 days of usual care. Hospital length of stay and all-cause 30-day hospital readmissions will be pulled from the billing database, [narcotic drug burden \(mean dose\) use on postoperative days 3 and 4 will be obtained from electronic medical records](#), and data on patient characteristics, medical history, surgical procedure, new onset atrial fibrillation and other post-operative complications will be retrieved from the IRB-approved Cardiothoracic Surgery database.

Purpose and Research Questions

The purpose of this randomized, controlled study is to learn if Reiki and manual therapy lead to differences in patients' postoperative clinical outcomes after first time coronary artery bypass graft (CABG) and/or cardiac valve surgery.

Research questions:

Compared to usual postoperative care, does Reiki and manual therapy:

1. Reduce negative emotions (depression and anxiety)?
2. Improve sleep?
3. Reduce pain?
4. Decrease hospital length of stay?
5. Reduce new onset atrial fibrillation?
6. Reduce 30-day hospital readmissions?
7. [Reduce total narcotic burden \(mean dose\)?](#)

Review of Literature

In clinical practice, Reiki was studied by multiple investigators for its therapeutic effects. In a 2009 systematic review, 12 trials (that used placebo vs. treatment) were included, and in 9 of the 12, Reiki had a significant therapeutic effect (VanerVaart et al, 2009). Of the 12 trials, when assessed for quality, 11 of 12 ranked poor in quality (VanerVaart et al, 2009), making it difficult to determine the value of Reiki in clinical practice. In a 2008 systematic review of trials of Reiki that included placebo vs. treatment, researchers reported that outcomes varied dramatically between studies (Lee, Pittler and Ernst, 2008). For example, of the 9 papers, 3 had an outcome of depression, 1 had outcomes of pain and anxiety, 1 studied anxiety in pregnant women, 1 studied functional recovery after stroke, 1 studied pain in patients with diabetic neuropathy, 1 studied pain and anxiety in women undergoing breast biopsy and 1 paper had outcomes of stress and hopelessness. Researchers concluded that trials for any one condition were scarce and replication studies were not completed. Further, most studies had methodological flaws (small sample sizes, inadequate study design) and in one study, researchers failed to provide results between groups on depression, their primary outcome (Lee, Pittler and Ernst, 2008). In a final integrative review that included papers from 1980 to 2006, Vitale (2007) also found that outcomes and patient populations varied widely. Outcomes included both acute and chronic pain, stress/relaxation/depression, wound healing, biological factors (hematocrit and autonomic nervous system), and anxiety /wellbeing. Vitale (2007) found that there was not 1 consistent definition of Reiki and that 6 of 16 studies failed to meet primary endpoints.

Only 1 paper was published of “healing touch” (definition was consistent with our definition of Reiki) in patients post CABG surgery (MacIntyre et al, 2008). Patients received usual care; visitors (distraction) therapy or healing touch during postoperative recovery and 6 outcomes were studied: postoperative length of stay, incidence of postoperative atrial fibrillation, use of anti-emetic medications, narcotic pain use, functional status and anxiety. Of outcomes, only anxiety was improved (decreased) among healing therapy subjects, compared to the other 2 groups. In sub-analysis, length of stay was reduced among outpatients who received healing touch, compared to placebo or visitor therapy, but there were no differences among groups for patients who were in-hospital on the day of surgery (MacIntyre et al, 2008). Finally, researchers assessed autonomic nervous system factors (heart rate, vagal tone, systolic, diastolic and mean blood pressures, breathing rate and cardiac sensitivity to baroreflex) among healthy volunteers. Of factors, only heart rate was different (lower) between Reiki and non-Reiki groups. Further, vagal tone trended to be lower in Reiki patients (and corresponded to lower heart rates) (Mackay, Hansen and McFarlane, 2004).

Thus, a review of the literature on Reiki therapy provided evidence that more research is needed. Most reports of comparative trials had small samples, used healthy subjects or patients with medical conditions that were different than our intended postoperative cardiac surgical population, or had methods that may have caused threats to internal validity of findings.

Integrative therapies have gained much support and interest in the literature as methods to help alleviate pain and anxiety (Anderson & Cutshall, 2007). However, very few studies revealed therapeutic benefits of massage therapy in patients post CABG surgery (Anderson & Cutshall 2007), including research conducted previously on this patient population at Cleveland Clinic (Albert et al., 2009) that include massage to arms, legs and back. Cardiac surgery patients undergo a long procedure, may experience back, shoulder, and neck pain, or generalized tension postoperatively (Anderson & Cutshall, 2007). In a pilot study (n=58), 1 session of 20 minutes of massage therapy offered between day 2 and 5 postoperatively reduced pain, anxiety and tension scores and patients provided positive feedback (Cutshall, et al, 2010). Although authors concluded that massage should be considered for the management of cardiovascular surgical postoperative healing and incorporated in post cardiac surgical units (Cutshall, et al, 2010), more research is needed, since it is not currently considered evidence-based therapy. In another study with a very small sample, researchers compared 15 minutes of hand massage to control care (hand holding) followed by 30 minutes of rest for 2-3 sessions in the first 24 hours following cardiac surgery. Patients who received hand massage had lower pain intensity, but vital signs were similar between groups (Boitor, et al, 2015). Although hand massage is a low-cost non- pharmacological intervention that can be safely completed at the bedside (Boitor, et al, 2015), the sample size was too small to provide generalizable evidence. Finally, in a randomized trial, pain and anxiety were assessed after 2 massage therapy or rest (usual care) sessions on day 3 or 4 and day 5 or 6 among 152 cardiac surgery patients (Braun, et al., 2012). The massage group demonstrated a reduction in both pain and anxiety. These studies demonstrate that massage therapy may play a significant role in supporting cardiac patients' wellbeing and healing and that it should be offered along with Reiki therapy to determine if the combination of therapies is more important than 1 complementary therapy alone.

Methodology

Design: Randomized, controlled non-blinded study

Study Groups: Adults who had first-time open heart or robotic-heart surgery involving coronary arteries, cardiac valves or aortic root (+ other procedures).

Inclusion criteria:

- Over 18 years of age
- Speaks English language and capable of reading and hearing.
- Up to 4 “To Come In” patients enrolled per day (2 standard care and 2 intervention group)
- Arrive for surgery from outpatient (home) environment.
- Scheduled for surgery (arrives in “To Come In” area) on Monday and Tuesday.
- Lives in one of 6 counties of Northeast Ohio, to ensure access post- discharge hospitalization.

Exclusion criteria:

- EPIC history of dementia, cognitive decline, Down's syndrome or other neurologic, psychological or congenital deficiency that impacts ability to make decisions about enrollment. EPIC assessment will occur during the process prior to approaching patients.
- Severe sight and hearing impairment despite assistive devices
- Cardiac surgery on a Wednesday, Thursday or Friday.
- Was not admitted to the hospitals for surgery via To Come In status on the morning of surgery.
- Prolonged intubation (over 48 hours), or reinsertion of an endotracheal tube during or before the intervention is initiated (will result in intervention withdrawal).
- Sedated due to new onset delirium.

Intervention

Reiki is a Japanese energy-based healing technique that has been utilized in the United States since the 1940's. The English translation of Reiki is universal vital energy that flows throughout and encompasses all living forms (Rand, 1991). Reiki is delivered by gentle hand placement either on or slightly above the body by certified Reiki practitioners. In this study, Reiki will be delivered first, for 15 minutes and will involve light placement of hands-on patients' head, chest, shoulders, hands, knees, and feet (~ 3 minutes to each body part).

Manual therapy techniques include light effleurage to head and feet (for 5 minutes; ~ 2.5 minutes to each body part) by the Reiki practitioner who delivered the Reiki therapy. For this research study, manual therapy techniques are defined as light effleurage without pressure.

Reiki and manual therapy will be delivered for 3 consecutive days beginning on the day after endotracheal tube removal. A holistic environment will be provided for healing to both groups.

- Rooms will be quiet, and doors will be closed during the 20 minutes of rest (usual care) or intervention, unless patients are in an ICU setting; in ICU, curtains will be drawn.
- Patients will lie down in bed in supine position or sit in recliner, inhaling through their nose and exhaling through their mouth with their eyes closed.

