Depression and anxiety: Depression and anxiety will be assessed using the *Brief Symptom Inventory*, a 12-item survey that provides subscales severity indexes for depression and anxiety. The *Brief Symptom Inventory* was internally consistent (reliable); in patients with ischemic heart disease (Doering, et al., 2010). The *Brief Symptom Inventory* has been used to assess depression and anxiety in multiple patient populations, including cardiac diseases, and results were found to predict mortality (Doering, et al., 2010). The survey uses simple statements and a 5-level Likert-type response set, ranging from 0, *not at all* to 4, *extremely*.

Pain: Pain is a subjective symptom best measured by self-report. Pain will be measured in 2 ways. (1) Pain intensity will be measured on a scale of 0-10 with a score of 0 for no pain and 10 for worst pain, as part of usual care. (2) Highest (worst) and lowest (least) pain in the past 24 hours will be assessed via pain scores recorded in EPIC.

Sleep: The Richards-Campbell Sleep Questionnaire (RCSQ) was developed in 2000 to overcome issues with other sleep questionnaires used in an acute or ICU setting. Permission was previously given to the mentor of this study ([name]) to use the tool unconditionally. This tool has 5 domains: sleep depth, falling asleep, number of awakenings, percent of time awake, and overall quality of sleep. It uses a visual analog

scale to measure domains of sleep and the composite score range is 0 to 100 (to reflect 0 to 100 mm). The RCSQ is calculated by dividing the sum of the total length in millimeters of the visual analog scale lines by 5. It is reliable with a Cronbach's alpha of .90 in 70 critically ill subjects (Richards, O'Sullivan & Phillips, 2000). It is short, simple, and easy to administer and analyze. This tool will take approximately 1 minute to complete.

Hospital length of stay: Data will be collected by analysts using EPSi administrative database.

New onset atrial fibrillation: Data will be retrieved from the Cardiothoracic Surgery database, led and managed by HVI Institute. It is IRB approved and data are collected on every open-heart surgery as part of the Society of Thoracic Surgery data collection, that Cleveland Clinic participates in. Data will be received in an excel file and encounter record numbers will be matched to questionnaire data for analysis.

All cause 30-day hospital readmission: Data will be collected by analysts using EPSi administrative database.

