Written consent will be acquired by patients before initiation of the research study. Research nurses or research coordinators, who are not involved in the intervention or in clinical patient care will administer the questionnaire packets preoperatively (in TCI) and after the last Reiki treatment or usual care day of the research intervention for the following data: anxiety and depression and sleep. After preoperative data collection, patients will be randomized to the usual care or intervention group: using envelopes with assignments (136 control subjects 136 experimental subjects); based on groups of 20. Packets will be created by a nurse from the Office of Research and Innovation and envelope assignments will not be shared with any researcher. Research nurses or research coordinators can assist patients with completion of baseline and post-intervention questionnaires, as desired.

Data retrieved from administrative, EPIC and cardiothoracic surgery databases will be requested using usual procedures, after patients have completed the study. The cardiothoracic surgery database is IRB approved.

Sample Size

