Pain, LOS and other continuous factors: will be compared between groups using analysis of variance models. In each of the models, normality of the outcomes will be evaluated and, if necessary, data will be transformed prior to analysis. Results will be back-transformed for presentation of mean differences with 95% confidence intervals.

Reduced new onset of atrial fibrillation and reduced 30-day hospital readmission are binary outcomes that will be evaluated using Pearson chi-square tests or Fisher exact tests, in the case of rare outcomes.

Exploratory analyses will evaluate the relationship between patient characteristics and outcomes and adjust treatment group differences for these factors using similar methodology. An analysis will be performed using SAS software (version 9.4; Cary, NC). A significance level of 0.05 will be assumed for all outcomes.

Feasibility

The facility has sufficient trained Reiki certified practitioners to provide these modalities safely and accommodate the sample size. Hand placements and manual therapy specific for this study will be conducive for this patient population and will not put the patient at risk. The facility does at least ten cardiac surgeries Monday through Friday specific for this study to meet criteria for sample size.

Limitations and Anticipated Problems

Patients may be off the floor, busy with another service, sleeping or too sick (worsening status, readmitted to the ICU, intubated and sedated) or nauseated to be approached to carry out the Reiki intervention, even after enrollment. Not all patients will receive 3 sessions. To make up for possible attrition, 10% will be added to the minimum sample size. Patients may refuse therapy (a rare occurrence) or may not complete questionnaire tools. Administrative and cardiovascular registry data will be used to collect most variables. If there is a delay in data collection or entry into the database, we may be delayed with analysis.

Human Subjects Protection

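### Postoperative events are listed as exclusion criteria although randomisation follows preoperative data collection, and no analysis set says whether such patients stay in the analysis

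*Combined protocol and SAP*

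**What the plan says.** Under Methodology, the exclusion criteria mix preoperative conditions with two items that can be known only after the operation: "Prolonged intubation (over 48 hours), or reinsertion of an endotracheal tube during or before the intervention is initiated (will result in intervention withdrawal", and "Sedated due to new onset delirium". Only the intubation item carries a consequence, and that consequence concerns the intervention. The delirium item carries none.

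Data Collection Procedures places allocation earlier in the patient's course: "After preoperative data collection, patients will be randomized to the usual care or intervention group". Baseline questionnaires are completed before surgery. Follow-up questionnaires are given "after the last Reiki treatment or usual care day of the research intervention", so usual care has a matching follow-up day.

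Limitations and Anticipated Problems expects that some enrolled patients will be "too sick (worsening status, readmitted to the ICU, intubated and sedated" and so unavailable for sessions. Its answer is: "Not all patients will receive 3 sessions. To make up for possible attrition, 10% will be added to the minimum sample size".

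Length of stay and readmission come from the administrative database. Atrial fibrillation comes from the cardiothoracic surgery database, in which "data are collected on every open-heart surgery". These data "will be requested using usual procedures, after patients have completed the study".

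Data Analysis gives models and tests. It defines no analysis set, no rule for withdrawn or excluded patients, and no method for missing follow-up scores.

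**The concern.** An exclusion criterion normally decides who enters a trial. Here some of the criteria can be met only by patients who, on the natural reading of the procedures, already hold an allocation. A data manager who applies the list literally would delete randomised patients because of how they fared after surgery. A colleague who reads the Limitations section would keep the same patients and count missed sessions. The analysis section does not say which of them is right.

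The trial is not blinded, and the one stated consequence has no defined meaning for a patient in usual care. Nothing requires the items to be applied alike in the two arms. If they are not, the groups compared are no longer those randomised. Prolonged intubation, reintubation and delirium plausibly bear on length of stay, so removing such patients could matter there, although the data would be available without the patient's participation.

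**Working it through.** **1. Timing of each listed event.** Sessions start on the day after the endotracheal tube is removed (Intervention section).

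| Event | Relative to allocation | Relative to first session |
|---|---|---|
| First intubation over 48 hours | After, if the envelope is opened before surgery | Always before |
| Reintubation before the intervention starts | After, if the envelope is opened before surgery | Always before |
| Reintubation during the intervention | After, on any reading | Not necessarily before |
| Sedation for new-onset delirium | After, if the envelope is opened before surgery | Before or after |

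The plan does not state the exact moment at which the envelope is opened, but it describes no later randomisation step. Even if allocation waited for extubation, the third row would still follow it. The first two rows precede any study treatment and cannot be caused by it. Imbalance in those rows could arise only by chance or from uneven application. Only the last two rows could also reflect an effect of treatment.

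**2. The plan's own sample size.** Inputs from Sample Size: lognormal scores, coefficient of variation 1.35, 30% reduction, correlation 0.25, two-sided 0.05, 80% power.

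- Log-scale SD = √ln(1 + 1.35²) = 1.0186; target difference = |ln 0.70| = 0.3567.
- The two-sample t-test needs 130 per group. Multiplied by (1 − 0.25²) = 0.9375, this is 121.9, so 122; adding one per group gives the stated 123.
- Power at 123 per group is 80.9%.
- 123 × 1.10 = 135.3, rounded up to 136. The allowance is 136 − 123 = 13 per group.

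The stated figures reproduce and are not in dispute.

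**3. What removal does to numbers.** The documents give no event rates, so these are assumed. If a share e per arm is removed on top of the planned 10% loss, 136 × 0.9 × (1 − e) patients remain per arm.

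| Assumed e | Remaining per arm | Power |
|---|---|---|
| 0% | 122.4 | 80.8% |
| 2% | 120.0 | 80.0% |
| 5% | 116.3 | 78.7% |
| 10% | 110.2 | 76.5% |

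If removals fall within the 10% allowance and there is no other loss, power stays at 80.8%. Loss of power is therefore a minor matter.

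**4. What removal does to the comparison.** Suppose a share f of an arm is removed, and the removed patients' mean outcome exceeds the mean of all patients randomised to that arm by d. The retained mean is then lower than the randomised mean by d × f/(1 − f). The between-arm comparison shifts by the difference of this quantity between arms. With equal f and equal d the shift is zero. If removal occurred in one arm only, f of 2%, 5% or 10% would give multipliers of 0.02/0.98 = 0.020, 0.05/0.95 = 0.053 and 0.10/0.90 = 0.111. For length of stay, that is the shift in days for each day of d. The documents supply neither f nor d for either arm, so neither size nor sign can be fixed. Recruiting 13 more patients per arm leaves the multiplier unchanged.

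**The case against.** The strongest reply is that the plan never says these patients leave the analysis. The stated consequence is withdrawal from the intervention, and the Limitations section describes very similar patients simply as people who miss sessions. That reading is open. It rests on inference, however, because the items stand under exclusion criteria, one of them has no stated consequence, and the analysis section is silent.

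Second, first prolonged intubation and early reintubation precede treatment, intubation status is an objective fact, and the matching follow-up day lets the items be applied in both arms. All of this stands and narrows the routes to bias. It leaves uneven application in a non-blinded trial, and events after sessions begin.

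Third, patients who are intubated or sedated at follow-up could hardly complete a questionnaire, so the exclusion would add little to the missing scores that would occur anyway. This stands for anxiety, depression and sleep. It does not reach length of stay, atrial fibrillation or readmission.

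Fourth, a reader might infer from the timing of the data request that only patients who finish the study are looked up in the databases. The documents do not support that: the sentence may describe timing alone. It also does not say that every randomised patient is covered.

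**Conclusion.** The point holds as an ambiguity with a practical consequence and should be fixed. Events that arise after surgery are labelled exclusions, at least one of them necessarily follows allocation, and no analysis set keeps the patients in. If the list is applied as written, randomised patients are dropped. The loss is avoidable mainly for length of stay, atrial fibrillation and readmission.

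A reader might go further and infer that the plan already excludes these patients from analysis, or that the result will be biased in favour of the intervention with a raised false-positive rate. The documents support neither. The consequence they state may mean only that sessions stop. They give no event rates, no outcome differences and no sign that removal would be one-sided, and equal removal of similar patients cancels. The size and direction of any bias are therefore unknown. The conclusion rests on the reading that allocation precedes surgery, except for reintubation during the intervention, where it needs no such assumption.

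**What to change.** - Reconcile the exclusion criteria with the Limitations section: keep preoperative eligibility in the criteria and list the postoperative events separately as events after randomisation. State the moment of randomisation. Whether and when sessions stop is a clinical matter on which no rule is proposed here.
- State that these events do not remove a patient from the analysis, and that every randomised patient is analysed in the assigned group.
- State that the database request covers every randomised patient, so that length of stay, atrial fibrillation and readmission are analysed for all.
- Record prolonged intubation, reintubation and delirium in the same way in both arms.
- Analyse the questionnaires with the planned analysis of covariance for all randomised patients with follow-up data, and report the number missing and the reasons by arm. A sensitivity analysis for missing scores, shifting imputed values until the conclusion changes, is optional.

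The cost is protocol wording and one event code per patient, with no added patients or visits. The drawback is some dilution from patients who receive no sessions. For scale, assume that a share w of the analysed intervention patients receives no session and no benefit, so that the log-scale effect becomes 0.3567 × (1 − w). With 123 per arm the standard error is 1.0186 × √0.9375 × √(2/123) = 0.1258. Power for a primary score is then 79.4% at w = 2%, 76.9% at 5% and 72.3% at 10%, against 80.9% with none. These shares are assumptions.
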